Statistical Analysis Plan (SAP) for the study

Amino Acid Transport Imaging of Parathyroid Adenomas with anti-3-[18F] FACBC

Principal Investigator: [name].

IRB00051415

NCT01574287

Date: 06/13/2019

Data obtained from image ([18F]fluciclovine PET/CT and [99mTc]Sestamibi Planar (Early and Delayed) and Delayed SPECT/CT) interpretation were analyzed using SPSS version 23 (IBM, Armonk, NY).

Histopathologic confirmation of resected parathyroid adenoma or hyperplasia was reference standard for truth. Descriptive analysis was carried out, and mean ± SD was reported as appropriate. Difference in means of uptake parameters for [18F]fluciclovine PET compared with [99mTc]sestamibi was determined using t-test. Statistical significance was set at p < 0.05.

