The specific hypothesis in this proposal is that amino acid transport in parathyroid adenoma and hyperplasia is upregulated compared with normal parathyroid tissue and that this elevated uptake can be exploited for lesion identification by use of PET amino acid radiotracer imaging. The most comprehensive manner to assess our hypothesis is to undertake a prospective pilot study in patients with biochemical evidence of primary hyperparathyroidism and who are scheduled for standard of care surgery and typical preoperative clinical imaging including ^{99m}Tc MIBI SPECT-CT.

We propose assembling a dedicated multidisciplinary team of experts in amino acid radiotracer synthesis and imaging as well as surgical therapy of hyperparathyroidism. Outcomes will be validated by direct comparison to truth as established by histology and surgical findings. We will also in Specific Aim 2, examine potential mechanisms of uptake via gene array, RT-PCR analysis and immunohistochemical techniques.

C. Study design and methods

Experimental design. We will undertake a study with 12 patients who have biochemical and clinical evidence of primary hyperparathyroidism and who are scheduled for routine surgery and preoperative imaging. The patients will serve as their own control. This study will not interfere with standard patient evaluation or delay therapy. Patients will receive one additional study using the amino acid analogue with *anti*-3-[¹⁸F]FACBC. Within the group of 12, we will choose 6 patients with low MIBI uptake and 6 with high uptake since amino acid uptake could also vary in each sub-population. Dynamic imaging will be performed for 60 minutes.

All patients will undergo routine preoperative imaging including dual phase ^{99m}Tc sestamibi scanning and other imaging as appropriate such as ultrasound, MRI, and/or contrast enhanced CT scanning.

We will investigate amino acid transport kinetics and conspicuity within parathyroid adenomas utilizing *anti*-3-[¹⁸F]FACBC PET-CT (Specific Aim #1). We will compare various uptake parameters to that of standard of care imaging with dual phase ^{99m}Tc sestamibi SPECT-CT and validate to truth via surgery and histologic analysis. Resected tissue will also undergo gene

array, RT-PCR analysis and immunohistochemistry as appropriate to investigate amino acid transport mechanism and other factors in uptake (Specific Aim #2). C.1 *anti*-3-[¹⁸F]FACBC Radiolabeling

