5. Positive serum or urine pregnancy test within 24 hours of imaging prior to injection of radiotracer (for women of childbearing potential per Radiology Department clinical guidelines)

E. Statistical Analysis.

Since this is a pilot study only descriptive statistics will be possible.

F. Adverse Event Reporting

Any patient death that may be due to the study procedure (i.e. severe radiotracer reaction), unanticipated problem, or protocol deviation/non-compliance would be promptly reported to the Emory IRB office. Additionally any patient death not associated with the study procedure or serious anticipated event (i.e. radiotracer allergy) will be reported to the Emory IRB and FDA upon continuing review. This radiotracer is studied under IND 72437 and monitoring will be performed per already agreed upon FDA guidance. Over 100 patients have been studied without adverse events.

G. Data and Safety Monitoring Plan (DSMP):

Patients will be monitored by the technologists and study nurse before and after the studies for any adverse events/reactions. They will be given contact phone numbers to call if they experience any problems (i.e. problems with the IV site, any allergic reaction symptoms). They will be followed routinely by their referring surgeon with clinical exams, and the PI will work with

the co-investigators and referring physicians to ensure that the patients continue to follow up as scheduled.

In addition, a DSMB who will consist of Drs. [name], [name], [name], [name], and [name] will meet formally if an adverse event has been reported. Any serious adverse events (see above) will be communicated by the PI to the Emory IRB using standard adverse event reporting forms.

H: Pharmaceutical, biologic, and device information

Radiation Dosimetry. The study will be approved by not only the Emory IRB but also the Radiation Safety Committee. The maximum number of PET studies a patient will receive in this protocol is 1 FACBC study.

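### The SAP applies a cross-tracer t-test at p < 0.05 where protocol Section E allows only descriptive statistics; pairing and the sestamibi measure are unspecified, and no analysis of FACBC uptake by MIBI group is named.

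*SAP*

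**What the plan says.** Protocol Section E consists of one sentence: "Since this is a pilot study only descriptive statistics will be possible".

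Protocol Section C (Experimental design) sets up the comparison and the sample. On the comparison: "We will compare various uptake parameters to that of standard of care imaging", with dual phase sestamibi SPECT-CT named as that imaging. On the design: "The patients will serve as their own control". On selection: "we will choose 6 patients with low MIBI uptake and 6 with high uptake", on the ground that amino acid uptake might differ between the two groups. Specific Aim 1 (Section B) asks, among other things, whether FACBC uptake varies with sestamibi avidity.

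Section C.4, item 2, defines the FACBC measures: SUVmax, SUVmean, total lesion activity and tumor-to-background values, at several times including 15, 30, 45 and 60 minutes. No section does the same for sestamibi.

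The SAP is dated 2019, and the protocol 2013. It is written in the past tense ("interpretation were analyzed using SPSS version 23"). Besides means and SDs it reports one comparison: "Difference in means of uptake parameters for [18F]fluciclovine PET compared with [99mTc]sestamibi was determined using t-test". It adds: "Statistical significance was set at p < 0.05". It lists the sestamibi data as "99mTc]Sestamibi Planar (Early and Delayed) and Delayed SPECT/CT". The MIBI groups do not appear in it.

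**The concern.** The comparison between tracers was planned. What the SAP adds is a significance test, which Section E had ruled out because the study is a pilot, and no reason for the change is given.

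The test is also not described well enough for its p-value to be interpreted. A difference in means needs a common scale, and none is defined. Data with two tracers in each patient call for a within-patient analysis, and the SAP says only that a t-test was used. Meanwhile the question for which the 6/6 selection was made, FACBC uptake in low-MIBI against high-MIBI patients, has no named analysis.

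At stake is a significance claim about two tracers that the protocol did not allow for and that a reader cannot check, together with a part of Specific Aim 1 that could go unreported.

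**Working it through.** **Inputs from the documents.** n = 12, as 6 low-MIBI plus 6 high-MIBI (6 + 6 = 12, which agrees); both tracers in each patient; threshold 0.05. The documents give no power, effect size, SD or within-patient correlation, so there is no plan figure to reproduce. Two-sided testing, equal SDs and the correlations (rho) below are assumptions.

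**Step 1: the texts side by side.**

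| Item | Protocol | SAP |
|---|---|---|
| Inference | Descriptive only (Section E) | t-test, p < 0.05 |
| Pairing | Patients are their own control (Section C) | Not stated |
| Comparator | Dual phase SPECT-CT (Section C) | Planar early, planar delayed, delayed SPECT/CT |
| Sestamibi uptake measure | Not defined | Not defined |
| MIBI groups | 6 low, 6 high; Specific Aim 1 asks about avidity | Not mentioned |

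The modality named in Section C has one counterpart in the SAP, the delayed SPECT/CT. The phase does not line up: dual phase in one document, delayed only in the other.

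**Step 2: what pairing changes, if the test was unpaired.** With unit SDs, the unpaired statistic on paired data is

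t = Dbar / sqrt((vS + vD) / (2n)),

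where Dbar ~ N(d, 2(1 - rho)/n), vS ~ 2(1 + rho) × chi-square(11)/11 and vD ~ 2(1 - rho) × chi-square(11)/11, compared with the critical value of t on 22 df. Numerical integration at d = 0 gives:

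| rho | True type I error (nominal 0.05) |
|---|---|
| -0.3 | 0.084 |
| 0 | 0.050 |
| 0.3 | 0.022 |
| 0.5 | 0.009 |
| 0.7 | 0.002 |

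A simulation of 200,000 samples agrees within 0.001. The unpaired test is therefore too strict when rho is positive and too lenient when it is negative.

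Power at rho = 0.5 for a difference of 1 SD: the SD of the within-patient difference is sqrt(2 × (1 - 0.5)) = 1, so the paired noncentrality is sqrt(12) = 3.46 on 11 df and power is 0.88. The unpaired test has power 0.70.

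**Step 3: precision of a descriptive or paired report.** The 95% CI half-width, in SDs of the quantity averaged, is t(0.975, n - 1)/sqrt(n):

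- n = 12: 2.201/3.464 = 0.64 SD
- n = 6: 2.571/2.449 = 1.05 SD

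**Step 4: should the tracer difference be split by MIBI group?** The groups are chosen on sestamibi uptake, which is one half of that difference. Under a median split of a normal variable with equal SDs, the group means of sestamibi lie at ±sqrt(2/pi) = ±0.798 SD. The low-minus-high gap in FACBC minus sestamibi is then 2 × 0.798 × (1 - rho), that is 1.6 SD at rho = 0 and 0.8 SD at rho = 0.5. At rho = 0, FACBC uptake is the same in both groups, so the whole gap comes from selection. Specific Aim 1 asks about FACBC uptake between groups, and a table of FACBC alone avoids the artefact.

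**The case against.** The best defence is that silence is not error. A paired t-test is a t-test, and the data may have been paired. Section C names SPECT-CT, so the comparator is not open among three acquisitions. Section C.4, item 3, already plans to correlate FACBC results with sestamibi imaging, and the SAP's descriptive analysis may have included the MIBI groups. The cross-tracer test was never meant to answer the group question in Specific Aim 1. The study is a pilot whose primary aim, presence and kinetics of uptake, does not rest on this test.

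Most of this stands, and it limits what can be claimed:

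- A reader might infer that the test was unpaired. The SAP does not say so, and the figures in Step 2 apply only if it was.
- A reader might infer that SUV was tested against sestamibi counts, so that the p-value reflects units. Section C.4 also provides tumor-to-background values for FACBC, and the SAP wording allows either, so this is not documented.
- A reader might infer that the 6/6 quota distorts or reverses the tracer difference relative to an unselected population. The difference does depend on the selected mix, but the documents do not give the share of low-MIBI patients in such a population or the difference within each group. Neither size nor sign can be derived, and the pilot does not claim to estimate it.

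The defence does not remove the conflict between Section E and the SAP. Nor does it supply the missing sestamibi measure or a named analysis by MIBI group. That the study is a pilot is Section E's own reason for not testing.

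**Conclusion.** The point holds as a conflict between the two documents plus three gaps in specification: pairing, a sestamibi measure on a shared scale (with the phase mismatch), and FACBC uptake by MIBI group. The conflict and the gaps can be read directly from the text and need no assumption.

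Their numerical effect does need assumptions. The departures from the nominal 0.05, and the loss of power from 0.88 to 0.70, rest on an unpaired test, equal SDs and assumed correlations. The documents do not establish that any reported p-value is wrong.

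The defect is moderate. It should be corrected, because otherwise a significance claim stands that the protocol excluded and the group question in Specific Aim 1 has no stated analysis. It does not touch the primary aim.

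**What to change.** 1. Drop the p < 0.05 claim. Report FACBC uptake parameters descriptively (n, mean, SD) for low-MIBI and high-MIBI patients separately, with the numbers achieved in each group, and overall. This brings the SAP back to Section E and addresses Specific Aim 1.
2. If the cross-tracer comparison is kept:
   - Use one named unitless lesion-to-background ratio, formed the same way for both tracers, from one named SPECT/CT acquisition and one FACBC time point. Do not compare SUV or total lesion activity with sestamibi measures.
   - Report the within-patient paired difference with a 95% CI, and state a rule for patients with several lesions.
   - Label it exploratory and post hoc, and record it as a departure from Section E. The SAP is retrospective, so an amendment now could not make it prespecified.
   - State that its size depends on the 6/6 selection, and do not interpret it by MIBI group.

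Cost: a short rewording of the SAP and a re-tabulation. There will be fewer p-values and wide intervals (half-widths as in Step 3). Ratios would have to be measured on the sestamibi images only if the comparison is kept and this was not already done; the documents do not say whether it was.
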